COMIRB Protocol

COLORADO MULTIPLE INSTITUTIONAL REVIEW BOARD
[name] [contact] [contact]

Protocol #: 16-1965

Project Title: Management of diabetic ketoacidosis in children: does early glargine prevent rebound hyperglycemia?

Short Title: "Early glargine in DKA"

Principal Investigator: [name]

Co-investigators: [name] [name]; [name], PhD

Version Date: 11/6/2017

I. Hypotheses and Specific Aims:

Hypothesis 1 (Primary outcome): Early administration of glargine in the treatment of DKA in children will result in reduced rebound hyperglycemia compared to those given standard-of-care management.

Specific Aim 1 (Primary outcome): To evaluate the rate of rebound hyperglycemia (serum glucose level of greater than 180 mg/dL (>10 mmol/L) within 12 hours after discontinuation of IV insulin) in children treated for diabetic ketoacidosis (DKA) with early glargine versus standard-of-care management.

Hypothesis 2: Early administration of glargine in the treatment of DKA in children will result in a reduced rate of recurrent ketogenesis compared to those given standard-of-care management.

Specific Aim 2: To evaluate the rate of recurrent ketogenesis (beta-hydroxybutyrate ≥ 1.5 mmol/L within 12 hours after discontinuation of IV insulin) in children treated for diabetic ketoacidosis (DKA) with early glargine versus standard-of-care management.

Hypothesis 3: The risk of hypoglycemia will not differ between those given early administration of glargine versus those given standard-of-care management:

- a. Early administration of glargine in the treatment of DKA in children will not increase hypoglycemic events compared to those given standard-of-care management.
- b. Rate of blood glucose decrease while on IV insulin in children with DKA will not be different between those given early administration of glargine versus those given standard-of-care management.
- c. Participants who received early glargine will not need more frequent reductions in the IV insulin rate than those given standard-of-care management.

Specific Aim 3: To determine the risk of hypoglycemia between those given early administration of glargine versus those given standard-of-care management.

- a. Assess the frequency of hypoglycemic events during treatment of DKA, and within 12 hours after discontinuation of IV insulin, in children given early glargine versus standard-of-care management.

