Type 1 diabetes mellitus (T1D) is one of the leading chronic diseases in childhood with an estimated prevalence of 1:400-500 individuals, and the incidence of type 1 diabetes mellitus is increasing (1,2). Diabetic ketoacidosis (DKA) remains the leading cause of morbidity and mortality in children with T1D (3). The risk of DKA in patients with known T1D is estimated to be 1-10% per patient year, however, those with new onset T1D have been shown to present in DKA in up to 65% of cases (4-6). Further, the rate of new onset T1D patients presenting in DKA increased by 55% from 1998 to 2012 in our center (Children's Hospital Colorado) (7) and the number of hospital visits for DKA nationally increased from roughly 80,000 in 1988 to about 140,000 in 2009 (8). In terms of overall healthcare burden, DKA is responsible for over 500,000 hospital days for adult and pediatric patients resulting in an estimated yearly direct and indirect cost of 2.4 billion USD (9,10).

One frequent complication in DKA associated with in-hospital mortality and longer intensive care stay is hyperglycemia; specifically, rebound hyperglycemia (serum glucose level of greater than 180 mg/dL (>10 mmol/L) within 12-24 hours after discontinuation of IV insulin) (11-13). This outcome has been shown to occur in approximately 40-90% of patients after transition from IV to subcutaneous insulin (11,14,15) and can lead to ketogenesis and recurrence of DKA (16).

Treatment of DKA involves intravenous (IV) fluids and IV insulin to resolve the acidosis, hyperglycemia, and hypovolemia, and frequently requires close monitoring in an intensive care unit. Prolonged treatment with IV insulin not only increases demands on nursing staff, through the need for more frequent blood glucose monitoring, but also increases the risk of hypoglycemia (17). Current guidelines from the American Diabetes Association (ADA), the Joint British Diabetes Societies, and the International Society of Pediatric and Adolescent Diabetes (ISPAD) advise transition to subcutaneous insulin (and discontinuation of IV insulin) once full resolution of ketoacidosis is achieved. However, they include the option to continue a long-acting insulin analog

during the initial management of DKA in patients with established diabetes to reduce the frequency and severity of rebound hyperglycemia and ketogenesis (16-18).

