Our emergency department sees an average of 150 cases of DKA per year and our center is involved in multiple clinical trials studying DKA management in children. Further, members of our group have been influential in developing a hospital-wide DKA protocol that is utilized both in the emergency department as well as in the inpatient setting to establish standardized and safe clinical care.

Glargine administration early in DKA management has been studied by our colleagues at University of Colorado Hospital in adults (with direct involvement from our co-mentor [name]). This group found that early administration of glargine in DKA resulted in a decreased rate of rebound hyperglycemia (33.3% versus 93.5%, $p < 0.001$ (14)). This data cannot be directly translated into the care of children in DKA, however, given the increased risk of complications in children such as cerebral edema and adverse events related to severe hypoglycemia. Therefore, without good pediatric data, the timing of glargine administration during the management DKA in children is left up to the discretion of the Diabetes Care Team and is, therefore, variable. Over the past 3-4 years, giving early glargine in DKA in children appears, anecdotally, to work well in the transition to subcutaneous insulin. It is viewed by many Diabetes providers to be a practical method and many are comfortable with this technique.

No data looking exclusively in children exist on whether early glargine administration in DKA management results in reduced rates of rebound hyperglycemia, is protective against recurrent ketogenesis, or how this relates to the risk of hypoglycemia. Further, no data exist on use of CGM technology in children treated for DKA. This detailed information will provide novel knowledge of blood glucose response both during treatment of DKA, and in the immediate phase following resolution of DKA, and help broaden our understanding of type 1 diabetes. CGM use in the hospital may also reduce the risk of hypoglycemic events and therefore improve patient safety.

IV. Research Methods:

A. Outcome Measure(s):

Primary outcome: Rate of rebound hyperglycemia within 12 hours (or until time to hospital discharge if less than 12 hours) after discontinuation of IV insulin on glucometer.

- Percent of patients with blood glucose > 180 mg/dL.
- Median blood glucose.

Secondary outcomes:

1. Rate of rebound hyperglycemia (as described in primary outcome) on CGM.

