- Upon diagnosis of DKA patients will begin rehydration with standard fluid therapy using an initial IV bolus of 10mL/kg of 0.9% saline.
- Fluid boluses may be repeated at the discretion of the treating physician to restore hemodynamic instability.
- During initial therapy, study personnel will obtain informed consent. .
- Participant Data: basic information such as name, date of birth, race/ethnicity, and diagnosis will be collected.
- Randomization:
 - We will use a blocked, stratified randomization scheme to allocate participants 1:1 to treatment groups. Randomization will be stratified within new onset and existing T1D patients to ensure balance across treatment groups.
 - Ideally, randomization will occur during the initial fluid bolus, however, if this is not possible then the patient will be treated with the standard DKA protocol for this study site until consent is completed, but not beyond the time frame outlined in the exclusion criteria.
 - Participants will be randomized into one of two groups:
 - 1. Early glargine, study group (N ~ 25):**
 - a. Administer glargine SQ x 1 when pH \geq 7.10.
 - b. Primary investigator and/or on-call co-investigator to determine glargine dose:
 - i. New onset T1D: 0.3 units/kg
 - ii. Established T1D: use home total daily dose (TDD) of long-acting insulin (or TDD of basal if on an insulin pump), converted to glargine equivalents.
 - 2. Standard-of-care, control group (N ~ 25):**
 - a. Administer glargine SQ x 1 at time of correction of acidosis (venous pH \geq 7.3 and serum bicarbonate \geq 18 or BHB \leq 1) and discontinuation of IV insulin.
 - b. Primary investigator and/or on-call co-investigator to determine glargine dose as described above.
- After initial fluid bolus(es), standard insulin therapy begins with a continuous infusion of IV regular insulin at a rate of 0.1 units/kg/hr.
- Ongoing rehydration is established using IV fluids with $\frac{3}{4}$ normal saline at a standard rate of 1.5 x maintenance unless this is determined to be harmful by the primary attending physician.
- Potassium replacement is provided using IV fluids containing potassium acetate and potassium phosphate.
- When serum glucose concentration declines below 250 mg/dL, dextrose (5-12.5%) is added to the IV fluids to maintain serum glucose between 100 mg/dL and 200 mg/dL.

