- If more than 12.5% dextrose IV fluids are needed to maintain serum glucose between 100 mg/dL and 200 mg/dL, the IV insulin rate will be decreased by 0.01 units/kg/hr.

Laboratory Monitoring during DKA treatment:

- Blood glucose concentration is obtained at presentation and hourly while on IV insulin using a point-of-care glucometer or serum measurements.
- Venous pH, serum electrolytes (Na, K, Cl, HCO₃, BUN, creatinine) are obtained at presentation and then every 2-4 hours while on IV insulin.
- Serum beta-hydroxybutyrate (BHB) will be obtained at presentation and then every 6 hours while on IV insulin until \leq 1.0 mmol/L.
- HbA1c will be obtained at presentation.

Continuous Glucose Monitoring (CGM): An option to have CGM sensor placed will be discussed with participant and/or primary guardian. The CGM system used during this study will be the Abbott FreeStyle Libre Pro Flash® Glucose Monitoring System (Figure 2).

Figure 2: Abbott FreeStyle Libre Pro Flash® Glucose Monitoring System:

<http://www.freestylelibrepro.us/blood-glucose-monitoring-device.html>

The FreeStyle Libre Pro® uses a small low-profile sensor approved for up to 14 days of wear in the USA by the FDA and has shown an average mean absolute relative difference (MARD) of 11.4% over 14 days of continuous wear. The Libre is also marketed as being free from interference with acetaminophen, eliminating this as a concern in our population as this is a common medication used in pediatrics. Further, this system does not require calibration and is blinded from the participant. Data will be available to study personnel at time of download after 1 week of wear.

CGM protocol:

- Following informed consent, an area on the back of the upper arm will be cleaned with an isopropyl alcohol solution and the CGM sensor system will be placed by trained study personnel.
- The CGM sensor placement will ideally occur after initial rehydration has been established, however, if this is not possible the CGM can be placed on the participant at any time during the initial 12 hours of DKA management.
- The CGM sensor will remain on the participant for the duration of hospitalization and an additional week following discharge.
- If a CGM sensor malfunctions during the participant's hospitalization, a new sensor can be replaced by study personnel as soon as possible following knowledge of the malfunction.

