- Participants will return the CGM sensor to study personnel after approximately 1 week (see section C.2.3 below).

C.2.2. Upon resolution of DKA:

- When venous pH ≥ 7.3 and serum bicarbonate ≥ 18 mmol/L (or BHB < 1.0 mmol/L) and participant is awake and alert, he/she will be transitioned to subcutaneous insulin:
 - Discontinuation of IV insulin.
 - Initial subcutaneous dosing:

- Glargine: 0.3 units/kg SQ x 1 for new onset T1D (or home glargine equivalent dose for established T1D) – if not already given as part of the Early Glargine/study group (see section C. 2.1 for dosing).
- Lispro: 0.2-0.6 units/kg/day, administered using a standard Multiple Daily Injection (MDI) regimen: before meals or as needed for hyperglycemia (but not more often than every 4 hours).
- The on-call physician can override the above dosing based on clinical judgment.
- **Insulin pump:** Participants with established T1D who are managed with an insulin pump at baseline will have the option to either:
 1. NOT reconnect or use their insulin pump for 24 hours after the protocol glargine dose was administered and will receive standard MDI therapy during that time with dosing determined by the inpatient diabetes team or study personnel. They can resume full home insulin pump use after 24 hours following glargine administration.
 2. Reconnect their home insulin pump to use for BOLUSING ONLY with meals and snacks and will not use their basal rate (set a temporary basal rate of 0%) for 24 hours after the glargine dose was administered. They can resume full home insulin pump use after 24 hours following glargine administration.

Laboratory monitoring upon resolution of DKA:

- Blood glucose concentration obtained before meals, at bedtime, and at 0200 using point-of-care glucometer.
- Serum BHB obtained every 6 hours until ≤ 1.0 mmol/L or at any time if blood glucose on glucometer is > 300 mg/dL for two consecutive measurements.
- Participants who remain hospitalized over 24 hours will have a BHB drawn at 12-18 hours after discontinuation of IV insulin to assess for late-recurrent ketosis.

Table 1: Summary of laboratory monitoring:

| Data: | During DKA | Upon resolution of DKA |
|---------------------|--|--|
| POC glucose (mg/dL) | At presentation and hourly | Before meals, at bedtime, at 0200 |
| BMP | At presentation and approx. every 2-4 hours | As needed |
| HbA1c (%) | At presentation | |
| VBG | At presentation and approx. every 2-4 hours | As needed |

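### The on-infusion glucose target reaches 200 mg/dL while any later value above 180 mg/dL counts as rebound, so the primary endpoint mixes persistence of a permitted level with a rise after stopping

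*Combined protocol and SAP*

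**What the plan says.** Specific Aim 1 (section I) sets out to compare the "rate of rebound hyperglycemia (serum glucose level of greater than 180 mg/dL (>10 mmol/L) within 12 hours after discontinuation of IV insulin". Section IV.A makes this the primary outcome, assessed "within 12 hours (or until time to hospital discharge if less than 12 hours) after discontinuation of IV insulin on glucometer", and lists two summaries: "Percent of patients with blood glucose > 180 mg/dL" and the median blood glucose. Neither place asks for a reference value, a rise or a repeat reading.

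In both arms, section IV.C.2.1 says that once glucose has declined below 250 mg/dL, "dextrose (5-12.5%) is added to the IV fluids to maintain serum glucose between 100 mg/dL and 200 mg/dL". Section IV.C.2.2 gives the conditions for ending the infusion: venous pH, and bicarbonate or BHB, "and participant is awake and alert, he/she will be transitioned to subcutaneous insulin". No glucose level is among them.

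Two monitoring rules also matter. On the infusion, "Blood glucose concentration is obtained at presentation and hourly while on IV insulin". Afterwards, "Blood glucose concentration obtained before meals, at bedtime, and at 0200 using point-of-care glucometer".

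**The concern.** The top fifth of the permitted on-infusion band, from 180 to 200 mg/dL, lies above the line that defines an event once the infusion stops. A child can be exactly where the protocol wants glucose to be, stay level or drift down, and still be scored as rebound at the next check. A child who stops above 200 mg/dL and is falling steadily can be scored too.

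The title asks whether early glargine prevents rebound, which is a question about what happens after IV insulin stops. A null result could mean that glargine did not prevent a rise, or that many children in both arms were above the line already. A positive result could reflect lower glucose before the stop, because the early arm receives glargine during the infusion, and not a smaller rise after it. Nothing else in the plan separates these readings on the primary data. The median glucose is a post-stop level with no starting reference, and the logistic regression in section VII adjusts for BMI, sex, age and diabetes status but not for glucose at the stop.

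**Working it through.** **Inputs.** From section VII: 30% events with early glargine, a 40-point absolute difference (so 70% in controls), alpha 0.05, 80% power, a chi-squared test and 24 to 25 per arm. From section IV.C.2.1: a target band of 100 to 200 mg/dL. The share of children carried over above 180 mg/dL is not in the documents and is assumed below.

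**The plan's own figure.** With a two-sided test, pooled variance and no continuity correction:

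n per arm = [1.96 × √(2 × 0.5 × 0.5) + 0.842 × √(0.3 × 0.7 + 0.7 × 0.3)]² / 0.40² = (1.386 + 0.546)² / 0.16 = 23.3, rounded up to 24. The total is 48, as stated.

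Power at 24 per arm: z = (0.40 × √24 − 1.96 × 0.707) / 0.648 = 0.885, which gives 81%.

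**Reading A: 30% v 70% are rates of a true rise.** Let q be the share of children without a rise who are still scored because they persist above 180 mg/dL. The observed rate is p + (1 − p)q. If q is equal in both arms, the observed difference is 0.40 × (1 − q). If stop values were spread evenly over the band, and every child above 180 still read above it later, q would be 20/100 = 20%. This is an illustration only, so a range is shown.

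| Assumed q | Early | Control | Difference | Power, 24 per arm |
|---|---|---|---|---|
| 0 | 30% | 70% | 40 points | 81% |
| 10% | 37% | 73% | 36 points | 72% |
| 20% | 44% | 76% | 32 points | 63% |
| 30% | 51% | 79% | 28 points | 53% |

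For q = 20%: z = (0.32 × √24 − 1.96 × 0.693) / 0.655 = 0.32, which gives 63%.

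**Reading B: 30% v 70% already count any value above 180.** The observed contrast stays at 40 points, with 81% power and a total of 48. The implied contrast in true rises is then larger: at q = 10% it is (0.30 − 0.10)/0.90 = 22% v (0.70 − 0.10)/0.90 = 67%, or 44 points; at q = 20% it is 12.5% v 62.5%, or 50 points.

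**Unequal q, starting from reading A.** With q of 0 in the early arm and 20% in controls, the rates are 30% v 76%, and the contrast widens to 46 points. With 20% in the early arm and 10% in controls, they are 44% v 73%, or 29 points.

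**A tempting alternative endpoint.** Suppose an event counted only when a value above 180 followed one at or below 180. Under reading A with q = 20% the rates would be 0.8 × 30% = 24% v 0.8 × 70% = 56%. That is the same 32 points, and the mirror image of 76% v 44%, so power is again 63%. It would also score a child going from 185 to 400 as no rebound and one going from 178 to 181 as rebound.

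**The case against.** The strongest reply is that the absolute threshold is the protocol's declared and cited definition. Section II describes "rebound hyperglycemia (serum glucose level of greater than 180 mg/dL (>10 mmol/L) within 12-24 hours after discontinuation of IV insulin" and attaches the 40 to 90% literature rate to it. Section III reports the adult rates of 33.3% v 93.5% under the same term, and section VII states its 30% for that outcome. On the documents' own presentation, children carried over above 180 are already inside the planning rates, and adding q would count them twice. This stands, and it removes any firm claim of lost power.

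A reader might also infer that children above 180 at the stop are events in both arms whatever glargine does. The documents do not support that. A later glucometer reading must still exceed 180, scheduled checks are few, and lispro may be given before meals or for hyperglycemia. Whether a child at 195 has come down by the next check may itself depend on treatment. Equal q is likewise unproven, because early glargine is given before the infusion stops.

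Finally, some relevant data are planned: the median glucose, and CGM time and area above 180 with trajectories during and after treatment. CGM is optional, however, and none of these summaries relates a post-stop glucometer value to the child's own value at the stop. The overlap, and the mixing of persistence with a rise, remain. The reading of the stop criteria rests on the printed text; Figure 1 was not available for this review.

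**Conclusion.** The point holds as one of interpretation. The target band and the event threshold overlap between 180 and 200 mg/dL, glucose at the stop enters neither the event definition nor the printed stop criteria, and a child whose glucose never rises can be a primary event. Either outcome of the trial is therefore hard to read as evidence about rebound.

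A reader might go further and infer that the arm contrast shrinks and the trial is underpowered. That is not shown. Differences of 36, 32 and 28 points, with power of 72, 63 and 53%, need two assumptions: that 30% v 70% excluded carried-over children, and that carry-over is equal between arms at 10, 20 or 30%. Under the definition the documents use throughout, 40 points and about 81% power stand. If carry-over differs by arm, the contrast could move either way.

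**What to change.** Keep any value above 180 mg/dL as the primary analysis. Take the last hourly glucose on IV insulin, which is already collected, and add three things to section VII:

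1. Report that value by arm.
2. In the planned analysis set (confirmed type 1 diabetes, under the inclusion criteria), tabulate by arm children at or below 180 v above 180 at the stop, crossed with any later value above 180.
3. Pre-specify one sensitivity analysis over all analysed children in which an event needs a post-stop value that is both above 180 and above the child's own last on-infusion value. If it disagrees with the primary result, qualify any wording that early glargine prevents rebound.

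Do not restrict the analysis to children at or below 180 at the stop, and do not rest the conclusion on the stop value alone: it is measured after randomization and early glargine may change it.

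The protocol should also acknowledge the overlap and reconcile sections IV.A and IV.C.2.1. No glucose target is proposed here.

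The cost is one definition, one table and one test on existing data, with no change to treatment or sample size. The downsides are that treatment may affect the reference value, that this value may be a serum or a glucometer measurement while the outcome is on glucometer, and that a rise of a few mg/dL across 180 still counts.

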 - Percent of patients with blood glucose > 180 mg/dL.
 - Median blood glucose.
 - Percent of time with blood glucose > 180 mg/dL.
2. Rate of recurrent ketogenesis (serum beta-hydroxybutyrate \geq 1.5 mmol/L) within 12 hours (or until time to hospital discharge if less than 12 hours) after discontinuation of IV insulin.
 - Rate of late-recurrent ketogenesis (serum beta-hydroxybutyrate \geq 1.5 mmol/L) 12-18 hours after discontinuation of IV insulin for participants who remain hospitalized for over 24 hours.
3. Frequency of hypoglycemic events while on IV insulin (and within 12 hours after discontinuation of IV insulin) on glucometer or CGM.
 - Glucometer: percent of patients with blood glucose < 70 mg/dL (+/- 2 hours of an "index" hypoglycemic event).
 - CGM: % of time with blood glucose < 70 mg/dL.
4. Rate of blood glucose decrease while on IV insulin on glucometer and CGM within the following time points: 0-2 hours, 2-4 hours, 4-6 hours, >6 hours.
5. Number of participants who needed a decrease in their IV insulin rate (secondary to hypoglycemia).
6. Feasibility of using CGM as a tool for glucose monitoring in DKA.
 - Percent of CGM failures during treatment of DKA.
 - Correlation of CGM to POC glucose monitoring during DKA.

B. Description of Population to be Enrolled:

Eligible patients will be enrolled from Children's Hospital Colorado Emergency Department; a large tertiary care ED and level I trauma center in Aurora, Colorado. These will be patients with either a known diagnosis of T1D presenting in DKA or a new diagnosis of T1D presenting in DKA (see inclusion criteria). Patients will be enrolled either by the PI or a member of the study team (who will be available between the hours of 8:00 am and midnight). Depending on study team member availability, and due to the variability of time of presentation to the ED, patients who present outside of these hours may not be able to be enrolled into the study.

In this study we aim to approach 100 participants, both males and females aged 6-17.99 years, who present in DKA. Assuming 80% of participants approached will be eligible to participate and 60% of eligible subjects will consent to participate, this provides at least 48 subjects, which is needed for 80% power to detect an absolute difference of 40% difference in the rate of rebound hyperglycemia.

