- Lab collection: serum glucose, serum bicarbonate, serum sodium, serum chloride, serum potassium, serum blood urea nitrogen, serum creatinine, and serum beta-hydroxybutyrate will be obtained using standard venipuncture methods per hospital policy by trained staff. These measurements will be determined using standard methods in the Children's Hospital Colorado core laboratory. Blood glucose and beta-hydroxybutyrate will also be obtained using a point-of-care meter per hospital policy or at the Barbara Davis Center.

DKA protocol: Aside from the timing of glargine administration, all other treatment of DKA will be per the standard hospital DKA protocol (clinical care guidelines) at Children's Hospital Colorado. Available at: <https://ccguidelinesportal.childrenscolorado.org/guidelines/>

Glargine administration: This is a long-acting insulin analog which could theoretically increase the risk of hypoglycemia during its duration-of-action (20-24 hours). However, this is standard therapy for type 1 diabetes management with a long history of safe use. As such, study participants will receive glargine regardless of which study group they are randomized to; the only difference being the timing of glargine administration. Further, one of our secondary outcomes is to determine the risk of hypoglycemia between those given glargine early in DKA management versus those given glargine at time of DKA resolution.

CGM data collection: Wearing a CGM will be optional for study participants and included in the protocol as funding allows. The CGM sensor will be placed by trained study personnel to reduce risk of injury and/or sensor malfunction and to improve compliance. The CGM data will be downloaded after 1 week using standard industry software by trained staff or study personnel and the information stored in a locked study office.

Plan to minimize risk:

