1. **Participant Data:** Collection of patient data always holds a small risk of data breach. All research staff will be trained in good clinical practice and HIPAA. Any paper PHI will be stored in a locked study office and all electronic data records maintained by the study investigator for analysis will be password protected. Participants will be assigned a study number and de-identified datasets using only the study number will be used for analysis. This study number will be linked to the participant's PHI through a table accessible only to the PI, co-investigators, and research staff. Any other electronic or paper records which could be linked to the participant record or medical chart will be deleted or destroyed. PHI will not be connected to the data used in any manuscript or publication.
2. **General:** An experienced Diabetes Team (Barbara Davis Center) is routinely consulted on all patients with type 1 diabetes who present to Children's Hospital Colorado and is closely involved in their care throughout the hospitalization with regard to DKA management, blood glucose monitoring, and subcutaneous insulin dosing. The primary Diabetes Team routinely dictates when glargine is administered and at what dose. See "Subcutaneous insulin injection" section for additional details.
3. **Hypoglycemia:** blood glucose levels will be monitored closely throughout the hospitalization and hypoglycemic events will be treated per standard hospital hypoglycemia protocol. It is routine to monitor blood glucose hourly while on IV insulin and at least 4 times per day once off IV insulin. Once discharged from the hospital, participants will be instructed to check blood glucose levels at least 4 times per day and to call the Barbara Davis Center with any hypoglycemia issues or concerns.
4. **Venipuncture to draw blood for laboratory evaluation:** Venipuncture will be performed by clinical staff with experience with venipuncture to reduce the risk of pain and/or infection. Gloves will be worn and the area of skin cleaned per hospital policy to prevent risk of infection.

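### Secondary outcome 3 stops counting hypoglycemia 12 hours after IV insulin ends, short of the 20-24 hour glargine risk period the protocol names, and covers less of that period in the control arm

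*Combined protocol and SAP*

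**What the plan says.** Section IV.A (Outcome Measure(s)), secondary outcome 3, is "Frequency of hypoglycemic events while on IV insulin (and within 12 hours after discontinuation of IV insulin) on glucometer or CGM". On the glucometer it is the percent of patients below 70 mg/dL; on CGM it is the percent of time below 70 mg/dL. Section I, Specific Aim 3a, sets the same limit: "Assess the frequency of hypoglycemic events during treatment of DKA, and within 12 hours after discontinuation of IV insulin".

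Section IV.D (Glargine administration) says that glargine "could theoretically increase the risk of hypoglycemia during its duration-of-action (20-24 hours". The same paragraph offers a secondary outcome as the way to determine hypoglycemia risk between the arms.

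The arms differ in when glargine is given (Section IV.C.2.1, Randomization). In the control arm the instruction is "Administer glargine SQ x 1 at time of correction of acidosis", together with stopping IV insulin. In the early arm the dose is given once pH reaches 7.10, while IV insulin continues until the resolution criteria in Section IV.C.2.2 are met.

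Monitoring does not end at 12 hours. Inpatient meter checks continue at meals, bedtime and 0200 (Section IV.C.2.2). For children who accept CGM, "The CGM sensor will remain on the participant for the duration of hospitalization and an additional week following discharge". After discharge, "participants will be instructed to check blood glucose levels at least 4 times per day" (Section IV.D, Plan to minimize risk). Severe hypoglycemia is an adverse event with no stated time window (Section V).

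**The concern.** The counting window is tied to the end of IV insulin, whereas the risk described in Section IV.D starts with the glargine dose. The design deliberately separates those two events in one arm and makes them coincide in the other. A window with a common anchor in both arms therefore takes in different portions of glargine's action.

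Hypothesis 3a says that early glargine does not increase hypoglycemic events. If late control-arm events fall outside the window while the corresponding early-arm events fall inside it, the arms can differ on outcome 3 even when the risk per glargine dose is the same. In addition, the control-arm rate, and the early-arm rate when the lead time is short, would not describe the whole risk period.

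The matter is relevant to the protocol's own rationale. Section IV.B justifies a pediatric trial partly by concern about hypoglycemia in hospital and in the ambulatory setting. Section IV.A gives recurrent ketogenesis a 12-18 hour extension but gives hypoglycemia none, and no reason is stated for the 12-hour limit.

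**Working it through.** The plan states no coverage figure, so there is none to reproduce. The check asks what share of glargine's action lies inside the outcome 3 window.

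**Inputs**
- Window: time on IV insulin plus 12 h after it stops (Section IV.A; Aim 3a).
- Duration of glargine action, D: 20 to 24 h (Section IV.D).
- Lead time from glargine to the end of IV insulin, T: 0 h in control (Section IV.C.2.1). It is positive in the early arm by design, but no value is given. **T is assumed** at 4, 8 and 12 h. T = 0 is the limiting case and equals control.

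**Formulas**
- Share counted = min(1, (T + 12)/D).
- Hours not counted = max(0, D − 12 − T).

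**Control arm**
- D = 24: 12/24 = 50% counted, 12 h not counted.
- D = 20: 12/20 = 60% counted, 8 h not counted.

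**Early arm**

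| Assumed T | Counted, D = 24 | Counted, D = 20 | Hours not counted (D = 24 / D = 20) | Excess over control, points (D = 24 / D = 20) |
|---|---|---|---|---|
| 0 h | 12/24 = 50% | 12/20 = 60% | 12 / 8 | 0 / 0 |
| 4 h | 16/24 = 67% | 16/20 = 80% | 8 / 4 | 17 / 20 |
| 8 h | 20/24 = 83% | 20/20 = 100% | 4 / 0 | 33 / 40 |
| 12 h | 24/24 = 100% | 100% (capped) | 0 / 0 | 50 / 40 |

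**Direction, by illustration.** Assume the same true risk of 20% over glargine's action in both arms and a constant hazard. Neither assumption comes from the documents. The risk seen inside the window is 1 − 0.8^(share counted).
- Control: 1 − 0.8^0.50 = 10.6% (D = 24); 1 − 0.8^0.60 = 12.5% (D = 20).
- Early arm, T = 4 h: 1 − 0.8^(16/24) = 13.8%; 1 − 0.8^(16/20) = 16.3%.
- Early arm, T = 8 h: 1 − 0.8^(20/24) = 17.0%; 1 − 0.8^1 = 20.0%.

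With identical true risks, the early arm appears to have more hypoglycemia.

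**The case against.** The strongest reply is that outcome 3 answers the question Aim 3a asks. Both arms are anchored to the same event and have equal time after the infusion, and the overlap of glargine with IV insulin, which distinguishes the early arm, is fully counted. This stands for Aim 3a read literally: a reader might infer that its comparison is biased as written, and the documents do not show that. The distortion arises when the target is risk over glargine's action. That target is nevertheless the protocol's own, since Section IV.D names the 20-24 hour period and refers the question to a secondary outcome.

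A reader might also infer that the later hours are unobserved. They are not. Inpatient meter checks go on, severe events are reported without a time limit and bear on the stopping criteria in Section V, and Section VII plans per-day CGM summaries, including time below 60 and 70 mg/dL, with a comparison between groups. These are partial substitutes: CGM is optional and subject to funding, post-infusion meter checks are sparse, and adverse-event reporting covers severe cases only. None of them enters outcome 3.

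Finally, a reader might infer that the window hides early-arm harm relative to control. The likely direction is the opposite. Early-arm events can also be missed when T is short, so absolute risk may be understated in both arms.

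**Conclusion.** The mismatch between a 12-hour count and a stated 20-24 hour risk period is clear from the text. In the control arm 40-50% of glargine's action falls outside outcome 3. That figure rests only on the protocol's duration and on glargine being given when IV insulin stops.

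The difference in coverage between arms follows whenever T exceeds zero, but its size cannot be fixed from the documents. It is 17-20 percentage points at an assumed 4 hours, and reaches 40-50 points at 12 hours. The percentages weight each hour of action equally, and the event rates shown are illustrative only.

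The likely bias runs against early glargine and against Hypothesis 3a. The point concerns one secondary outcome in a trial powered for rebound hyperglycemia; the primary outcome and its test are untouched. It warrants an inexpensive addition to the plan, not replacement of the 12-hour outcome.

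**What to change.** Keep the 12-hour result. Add to secondary outcome 3 and Aim 3a a between-arm summary of hypoglycemia over 0-24 hours from each participant's protocol glargine dose, specified as follows:
- Use inpatient meter values, and CGM where worn.
- Censor children without CGM at discharge, and report the number censored by arm.
- Show events by hours since glargine, separately on and off IV insulin. Meter checks are hourly only while on IV insulin, so the early arm's first hours after the dose are sampled more densely than the control arm's.

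Moving the cut-off to 24 hours after IV insulin stops would be a poorer remedy. Control would have 24 hours after glargine and the early arm T + 24 hours (32 hours at T = 8), so the windows would remain unequal. Section IV.C.2.2 also lets pump users resume full pump use 24 hours after glargine, which would fall inside the early arm's window. It would depend as well on home readings for which some children have no stated collection route: Section IV.C.2.3 describes return of the CGM, by mail for some established patients, and no study contact for those who decline it.

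The change affects counting and reporting only. Treatment, tests and visits stay as they are. The cost is a wording amendment and incomplete follow-up to 24 hours for children discharged early without CGM.
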